8.5.2. Secondary Analyses

The best overall response will be summarized by each response category as CR, PR, SD and PD by treatment arms. Fisher's exact test will be used to compare ORR and CBR between treatment arms. The 2-sided 95% CIs for ORR and CBR will be calculated based on exact method. The difference in OS between the treatment arms will be assessed using the log-rank test. Kaplan-Meier estimates and plots, hazard ratios and corresponding 95% CIs will be presented.

8.6. Safety Analysis

Safety will be evaluated by assessment of clinical laboratory tests, physical examination, 12-lead ECG, vital signs measurements and documented AEs as described in the Study Procedures Table ([Appendix 2](#)). All safety data collected on or after the date that study drug was first dispensed up to the date of last dose of study drug plus 30 days will be summarized by dose level (Phase 1b Dose Escalation) and visit where appropriate and by treatment group for subjects in the Safety Analysis Set. AEs occurred in pretreatment will be included in data listings.

8.6.1. Extent of Exposure

A subject's extent of exposure to GS-5829 and fulvestrant will be reported. Exposure data and study drug compliance will be summarized by dose level and treatment group for subjects in the safety analysis set.

GS-5829 compliance will be described in terms of the amount actually taken based on returned pill count relative to the amount that was dispensed (taking into account physician-prescribed reductions and interruptions).

Fulvestrant compliance will be described in terms of the number of doses actually administered relative to the expected number of doses planned.

8.6.2. Adverse Events

The focus of AE summarization will be on treatment-emergent AEs. Treatment-emergent AEs (TEAEs) are events in a given study period that meet one of the following criteria:

- Events with onset dates on or after the start of treatment and up to 30 days after the permanent discontinuation of the study treatment.
- AEs resulting in treatment discontinuation after the start of treatment.

AEs will be coded using the Medical Dictionary for Regulatory Activities (MedDRA) (<http://www.meddramsso.com>) with descriptions by System Organ Class (SOC), High-Level Group Term, High-Level Term, Preferred Term, and Lower-Level Term. The severity of AEs will be graded by the investigator according to the CTCAE, Version 4.03, whenever possible. If

a CTCAE criterion does not exist for a specific type of AE, the grade corresponding to the appropriate adjective will be used by the investigator to describe the maximum intensity of the AE: Grade 1 (mild), Grade 2 (moderate), Grade 3 (severe), Grade 4 (life threatening), or Grade 5 (fatal). The relationship of the AE to the study drug will be categorized as related or unrelated. TEAEs will be summarized by dose level (Phase 1b Dose Escalation) and treatment group. Summary tables will be presented to show the number of subjects reporting treatment-emergent AEs by severity grade and corresponding percentages.

Following summaries (number and percentage of subjects) of TEAEs will be provided:

- 1) All AEs
- 2) AEs related to study drug
- 3) AEs that are Grade ≥ 3 in severity
- 4) AEs leading to study drug modification (interruption/reduction)
- 5) AEs leading to study drug discontinuation
- 6) AEs leading to death
- 7) SAEs

Summaries of TEAEs (by SOC and PT) will be provided by dose level (Phase 1b Dose Escalation) and treatment group. A subject who reports multiple treatment-emergent AEs within the same Preferred Term (or SOC) is counted only once for that Preferred Term (or SOC) using the worst severity grade.

All AEs will be listed.

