8. STATISTICAL CONSIDERATIONS

8.1. Analysis Objectives and Endpoints

8.1.1. Analysis Objectives

The primary objective:

Phase 1b Dose Escalation

- To characterize the safety and tolerability of GS-5829 in combination with fulvestrant and exemestane in subjects with advanced ER+/HER2- BrCa
- To determine the MTD or RP2D of GS-5829 in combination with fulvestrant in subjects with advanced ER+/HER2- BrCa

Randomized Phase 2 Dose Expansion

- To evaluate the efficacy of GS-5829 in combination with fulvestrant compared to fulvestrant alone in subjects with advanced ER+/HER2- BrCa, as measured by PFS

Secondary objectives:

Phase 1b Dose Escalation

- To evaluate the pharmacokinetics of GS-5829 in combination with fulvestrant in subjects with advanced ER+/HER2- BrCa

Randomized Phase 2 Dose Expansion

- To evaluate the efficacy of GS-5829 in combination with fulvestrant compared to fulvestrant alone in subjects with advanced ER+/HER2- BrCa, as measured by ORR and CBR evaluated according to RECIST v. 1.1. ORR is defined as the proportion of subjects with response (CR or PR). CBR is defined as proportion of subjects with CR, PR, or SD that lasts for ≥ 24 weeks
- To evaluate the safety and tolerability of GS-5829 in combination with fulvestrant compared to fulvestrant alone in subjects with advanced ER+/HER2- BrCa
- To evaluate OS for subjects with advanced ER+/HER2- BrCa who received GS-5829 in combination with fulvestrant compared to fulvestrant alone

Exploratory objectives:

PRD

PRD

PRD

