8.9. Sample Size

The sample size of the Phase 1b Dose Escalation portion of the study will be determined based on the number of dose levels evaluated and the emerging drug-related toxicities, and may enroll up to approximately 30 subjects.

Approximately 120 subjects will be enrolled in the Randomized Phase 2 Dose Expansion portion of this study. Approximately 80 subjects will be randomized to receive GS-5829 in combination with fulvestrant and 40 subjects to receive fulvestrant alone in a 2:1 ratio. The sample size of 120 subjects will provide 88 events in total and greater than 90% power to detect the difference in PFS between the two treatment arms with 0.1 one-sided significance level, assuming a median PFS of 4 months for subjects who receive fulvestrant alone, a median PFS of 8 months in subjects who receive GS-5829 in combination with fulvestrant, accrual period of 9 months and total study duration of 19 months and a drop-out rate of 10% by 12 months. Within each stratum of naïve or progressed prior CDK4/6 inhibitor plus AI subjects, the power will be 80% with target number of 60 subjects (44 events).

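### Phase 2 AEs are compared by crude percentages although time at risk is likely to differ between arms; an event equally hazardous in both would look about 1.3 to 1.4 times as frequent with GS-5829 under the plan's own timetable

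*Protocol*

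**What the plan says.** A Phase 2 secondary objective in Protocol Section 8.1.1 is "To evaluate the safety and tolerability of GS-5829 in combination with fulvestrant compared to fulvestrant alone". Section 8.1.3 includes timing of onset and duration of AEs in the safety endpoint.

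For the AE analysis, Section 8.6.2 states: "Summary tables will be presented to show the number of subjects reporting treatment-emergent AEs by severity grade and corresponding percentages". It lists seven TEAE summaries, all as number and percentage of subjects, by dose level in Phase 1b and by treatment group. A subject counts once per term, at worst grade. An event is treatment-emergent if it starts between first treatment and 30 days after permanent discontinuation.

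Treatment has no fixed length. Sections 3.4 and 6.5 let it continue until progression, unacceptable toxicity, withdrawal or another listed reason. Sections 5.3.1 and 6.5 add that, in the combination arm, stopping either drug stops both.

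Section 8.9 sizes Phase 2 "assuming a median PFS of 4 months for subjects who receive fulvestrant alone, a median PFS of 8 months in subjects who receive GS-5829" plus fulvestrant.

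Neither document specifies an exposure-adjusted rate, a time-to-first-event analysis or a fixed-window summary for AEs. Section 8.6.1 summarizes exposure by treatment group but does not link it to AE counts. SAP Section 1 reports that the study stopped in Phase 1b, and SAP Section 7.1.6.1 keeps counts and percentages.

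**The concern.** A percentage of subjects with an event depends on both the event rate and how long each subject is observed. Here observation ends shortly after treatment, and treatment normally ends at progression. If GS-5829 delays progression as planned, its arm is observed longer and accumulates more events of every persistent kind, including those it does not cause.

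The crude table would then count part of the drug's benefit as toxicity. The distortion grows with efficacy, and it falls on an objective that asks for safety relative to fulvestrant alone. The exposure table would show that the arms differ in time on drug. It would not show how much of an AE difference that explains, because it carries no subject-level time to first event.

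**Working it through.** **Inputs.** From Section 8.9: medians 4 and 8 months, 80 v 40 subjects, 9-month accrual, 19-month duration, 10% drop-out by 12 months, one-sided alpha 0.1. From Section 8.6.2: the 30-day window. Assumptions that are not in the documents: exponential PFS, time on treatment equal to PFS, and an AE hazard *h* that is constant and equal in both arms.

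**The plan's own figures.** Section 8.9 says that 120 subjects "will provide 88 events in total and greater than 90% power to detect the difference in PFS".
- Power = Φ(√(D × 2/9) × ln 2 − 1.2816). For D = 88: 4.422 × 0.693 − 1.282 = 1.784, so 96.3%. For D = 44: 3.127 × 0.693 − 1.282 = 0.886, so 81.2%, against the stated 80% per stratum.
- Rates per month: λ = ln 2/4 = 0.1733 (control) and ln 2/8 = 0.0866 (combination); drop-out d = −ln 0.9/12 = 0.0088. With uniform entry, expected events are 35.0 + 53.9 = 88.9, against 88.

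The inputs therefore reproduce the stated design.

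**Crude AE percentage.** For a subject with follow-up F, window w and m = λ + d:

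P(F) = 1 − e^(−hw) + e^(−hw) × h/(h+m) × [1 − e^(−(h+m)(F−w))]

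This is averaged over F uniform from 10 to 19 months.

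**Worked case, h = 0.05 per month, w = 1 month.** Here 1 − e^(−0.05) = 0.0488.
- Control: m = 0.1821, h/(h+m) = 0.2154. The last exponential averages 0.0520. P = 0.0488 + 0.9512 × 0.2154 × 0.9480 = 24.3%.
- Combination: m = 0.0954, h/(h+m) = 0.3438. The last exponential averages 0.1507. P = 0.0488 + 0.9512 × 0.3438 × 0.8493 = 32.7%.
- The ratio is 1.34, an excess of about 8 points for an event that GS-5829 does not cause. (With w = 30/30.44 months the combination figure is 32.6%.)

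**Range.** Ratio of crude percentages, combination to control, with w = 30/30.44 months:

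| Control risk | 9-month accrual, 19-month cutoff, drop-out | Complete follow-up, drop-out | Complete follow-up, no drop-out |
|---|---|---|---|
| Rare-event limit | 1.43 | 1.77 | 1.85 |
| 5% | 1.41 | 1.70 | 1.78 |
| 10% | 1.39 | 1.64 | 1.71 |
| 20% | 1.36 | 1.53 | 1.58 |
| 30% | 1.32 | 1.44 | 1.48 |
| 50% | 1.24 | 1.28 | 1.30 |

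The first row is the ratio of mean time at risk: 8.49/5.95 months with the cutoff, 12.53/6.76 without cutoff or drop-out.

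**Sensitivity.**
- Extra stopping in the combination arm (assumed 10% to 30% by 12 months), under the 19-month timetable: 1.36 down to 1.19 for control risks of 5% to 30%.
- Events confined to the first 1, 2 or 3 months (h = 0.10, no drop-out): 1.00, 1.02 and 1.05.

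**Effect of the fix in the worked case.** Mean time at risk to first event is P/h: 0.243/0.05 = 4.86 months and 0.327/0.05 = 6.53 months. Both arms then show 5.0 first events per 100 patient-months. At Week 16 (3.68 months), one minus Kaplan-Meier is 1 − e^(−0.05 × 3.68) = 16.8% in both.

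**The case against.** Four objections deserve an answer.

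**Size.** A reader using only the two medians might infer a larger bias. With h/(h+λ) at 0.05 per month, 0.05/0.2233 = 22.4% v 0.05/0.1366 = 36.6%, a 14-point gap and a ratio of 1.63. That omits the 30-day window, drop-out and the 19-month duration, each of which pulls the ratio down. Under the plan's timetable it cannot pass 1.43. The larger range is not excluded, because no data cutoff for safety is stated and 19 months is a sample-size input. But it is not what the stated inputs imply.

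**Exposure.** A reader might also infer that the plan assumes treatment lasts twice as long with GS-5829. It does not; it assumes that median PFS doubles. Toxicity stops, and the rule that stopping one drug stops both, would shorten combination treatment relative to PFS. This stands and lowers the estimate.

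**Scope.** It would be too strong to say that safety as a whole rests on crude percentages. Section 8.6.1 reports exposure by arm, and Section 8.6.3 reports laboratory values by visit and allows worst grade up to a particular visit. The criticism fits the AE tables.

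**Consequence.** No between-arm AE test is planned, and Phase 2 was not started. Both are true. They argue for supplementary tables rather than replacement of the percentages, and they mean that no result is affected.

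**Conclusion.** The point holds for the Phase 2 AE comparison in the protocol. The stated summaries do not account for time at risk, the design expects that time to differ, and the bias runs against GS-5829.

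Under the sample-size timetable, the spurious ratio is about 1.3 to 1.4 for events with 5% to 30% control risk. It is about 1.5 to 1.8 only if every subject is followed to 30 days after treatment ends with no drop-out. It falls to 1.24 to 1.30 at 50% control risk and almost vanishes for early-onset events. These figures rest on exponential times, a constant hazard equal in both arms, and treatment time that tracks PFS. The absence of any AE summary that accounts for exposure or timing, despite Section 8.1.3, needs no model to show.

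The documents do not support reading this as a flaw in any reported finding. The SAP covers Phase 1b cohorts descriptively, and its percentages serve that purpose. The change is worth making if the Phase 2 plan is reopened or this section is reused.

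**What to change.** Keep the number-and-percentage tables. For Phase 2, add to Section 8.6.2:

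1. Exposure-adjusted incidence by arm for the seven listed summaries: subjects with a first event per 100 patient-months at risk. Time at risk runs from first dose to the first event or, if none, the earlier of data cutoff and 30 days after permanent discontinuation.
2. Cumulative incidence by arm at a fixed time such as Week 16, for Grade 3 or higher AEs and for SAEs, by Kaplan-Meier with subjects censored at the end of their time at risk.
3. A sentence saying that the crude percentages will be read alongside these when the arms are compared.

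State the data cutoff for the safety analysis as well, since the size of the bias depends on it.

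The cost is a few tables from onset and dosing dates already collected. Neither addition is free of assumptions. The exposure-adjusted rate presumes a constant hazard and, for early-onset events, dilutes the rate in the arm treated longer. The fixed-time estimate does not need a constant hazard, which is why the two are paired, but it treats leaving treatment as uninformative about later AE risk.

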8.6.3. Laboratory Evaluations

All central laboratory results will be listed. Selected laboratory data will be summarized using only observed data. Laboratory results and change from baseline at all scheduled time points will be summarized.

The focus of laboratory data summarization will be on treatment-emergent laboratory abnormalities. A treatment-emergent laboratory abnormality is defined as an abnormality that, compared to baseline, worsened by ≥ 1 grade in the period from C1D1 to 30 days after the last dose of study drug. If baseline measurement is missing, then any graded abnormality (i.e., an abnormality that is Grade ≥ 1 in severity) will be considered treatment emergent.

Hematology and serum biochemistry will be graded according to CTCAE 4.03 severity grade, when applicable. For parameters for which a CTCAE scale does not exist, reference ranges from the central laboratory will be used to determine whether a laboratory value is below, within, or above the normal range for the subject's age, sex, etc.

Hematology and serum biochemistry test results and their changes from baseline will be summarized by dose level (Phase 1b Dose Escalation), visit and treatment group. Laboratory abnormalities will be summarized for each relevant assay to show the number of subjects by CTCAE severity grade with corresponding percentages. For parameters for which a CTCAE scale does not exist, the frequency of subjects with values below, within, and above the normal ranges will be summarized. Subjects will be characterized only once for a given assay, based on their worst severity grade observed during a period of interest (e.g., during the study or from baseline to a particular visit).

Shift tables for hematology and serum biochemistry will be presented by showing change in CTCAE severity grade from baseline to the worst grade post-baseline. Separate listings and summaries will be prepared for laboratory abnormalities that are Grade ≥ 3 in severity.

8.6.4. Other Safety Evaluations

Dose limiting toxicities will be listed for all dose levels.

8.7. Pharmacokinetic Analysis

In the Phase 1b Dose Escalation portion of study, the plasma concentration of GS-5829 will be summarized by nominal sampling time using descriptive statistics by dose cohorts. Pharmacokinetic parameters will be determined using standard non-compartmental methods. Pharmacokinetic parameters (such as C_{max} and, AUC_{tau}), will be listed and summarized using descriptive statistics (e.g., sample size, arithmetic mean, geometric mean, coefficient of variation (% StD, median, minimum, and maximum) by dose cohorts. Plasma concentrations over time will be plotted in semi-logarithmic and linear formats as mean \pm StD, and median (Q1, Q3) if applicable. In the Randomized Phase 2 Dose Expansion portion of study, plasma concentrations will be summarized by nominal sampling time using descriptive statistics by treatment arm.

8.8. Biomarker Analysis

Descriptive statistics of baseline and change from baseline in biomarkers will be provided at each sampling time for all subjects, and by treatment arms.

PPD

8.9. Sample Size

The sample size of the Phase 1b Dose Escalation portion of the study will be determined based on the number of dose levels evaluated and the emerging drug-related toxicities, and may enroll up to approximately 30 subjects.

Approximately 120 subjects will be enrolled in the Randomized Phase 2 Dose Expansion portion of this study. Approximately 80 subjects will be randomized to receive GS-5829 in combination with fulvestrant and 40 subjects to receive fulvestrant alone in a 2:1 ratio. The sample size of 120 subjects will provide 88 events in total and greater than 90% power to detect the difference in PFS between the two treatment arms with 0.1 one-sided significance level, assuming a median PFS of 4 months for subjects who receive fulvestrant alone, a median PFS of 8 months in subjects who receive GS-5829 in combination with fulvestrant, accrual period of 9 months and total study duration of 19 months and a drop-out rate of 10% by 12 months. Within each stratum of naïve or progressed prior CDK4/6 inhibitor plus AI subjects, the power will be 80% with target number of 60 subjects (44 events).

9. RESPONSIBILITIES

9.1. Investigator Responsibilities

9.1.1. Good Clinical Practice

The investigator will ensure that this study is conducted in accordance with the principles of the Declaration of Helsinki (as amended in Edinburgh, Tokyo, Venice, Hong Kong, and South Africa), ICH guidelines, or with the laws and regulations of the country in which the research is conducted, whichever affords the greater protection to the study subject. These standards are consistent with the European Union Clinical Trials Directive 2001/20/EC and GCP Directive 2005/28/EC.

The investigator will ensure adherence to the basic principles of GCP, as outlined in 21 CFR 312, subpart D, "Responsibilities of Sponsors and Investigators," 21 CFR, part 50, 1998, and 21 CFR, part 56, 1998.

The investigator and all applicable sub-investigators will comply with 21 CFR, Part 54, 1998, providing documentation of their financial interest or arrangements with Gilead, or proprietary interests in the investigational drug under study. This documentation must be provided prior to the investigator's (and any sub-investigator's) participation in the study. The investigator and sub-investigator agree to notify Gilead of any change in reportable interests during the study and for 1 year following completion of the study. Study completion is defined as the date when the last subject completes the protocol-defined activities.

9.1.2. Institutional Review Board (IRB)/Independent Ethics Committee (IEC) Review and Approval

The investigator (or sponsor as appropriate according to local regulations) will submit this protocol, informed consent form, and any accompanying material to be provided to the subject (such as advertisements, subject information sheets, or descriptions of the study used to obtain informed consent) to an IRB/IEC. The investigator will not begin any study subject activities until approval from the IRB/IEC has been documented and provided as a letter to the investigator.

Before implementation, the investigator will submit to and receive documented approval from the IRB/IEC any modifications made to the protocol or any accompanying material to be provided to the subject after initial IRB/IEC approval, with the exception of those necessary to reduce immediate risk to study subjects.

9.1.3. Informed Consent

The investigator is responsible for obtaining written informed consent from each individual participating in this study after adequate explanation of the aims, methods, objectives, and potential hazards of the study and before undertaking any study-related procedures. The investigator must use the most current IRB or IEC approved consent form for documenting written informed consent. Each informed consent (or assent as applicable) will be appropriately signed and dated by the subject or the subject's legally authorized representative and the person conducting the consent discussion, and also by an impartial witness if required by local requirements. The consent form will inform subjects about genomic testing and sample retention, and their right to receive clinically relevant genomic analysis results.

9.1.4. Confidentiality

The investigator must assure that subjects' anonymity will be strictly maintained and that their identities are protected from unauthorized parties. Only subject initials, date of birth, another unique identifier (as allowed by local law) and an identification code will be recorded on any form or biological sample submitted to the Sponsor, IRB or IEC, or laboratory. Laboratory specimens must be labeled in such a way as to protect subject identity while allowing the results to be recorded to the proper subject. Refer to specific laboratory instructions. NOTE: The investigator must keep a screening log showing codes, names, and addresses for all subjects screened and for all subjects enrolled in the trial. Subject data will be processed in accordance with all applicable regulations

The investigator agrees that all information received from Gilead, including but not limited to the investigator brochure, this protocol, eCRF, the IMP, and any other study information, remain the sole and exclusive property of Gilead during the conduct of the study and thereafter. This information is not to be disclosed to any third party (except employees or agents directly involved in the conduct of the study or as required by law) without prior written consent from Gilead. The investigator further agrees to take all reasonable precautions to prevent the disclosure by any employee or agent of the study site to any third party or otherwise into the public domain.

